### **FUNDING:**

National Center for Research Resources and the National Center for Advancing Translational Sciences of the National Institutes of Health through Grant Number UL1TR001449. UNM CTSC: CTSC034-10

## CLINICAL TRIALS

Is this a clinical trial per the NIH definition of a Clinical Trial?  Yes  No

NIH Definition of a Clinical Trial:

A research study in which one or more human subjects are prospectively assigned to one or more interventions. An "intervention" is defined as a manipulation of the subject or subject's environment for the purpose of modifying one or more health-related biomedical or behavioral processes and/or endpoints. Examples include: drugs/small molecules/compounds; biologics; devices; procedures (e.g., surgical techniques); delivery systems (e.g., telemedicine, face-to-face interviews); strategies to change health-related behavior (e.g., diet, cognitive therapy, exercise, development of new habits); treatment strategies; prevention strategies; and, diagnostic strategies (which may include placebo or other control) to evaluate the effects of those interventions on health-related biomedical or behavioral outcomes.

**Use the following four questions to determine the difference between a clinical study and a clinical trial:**

- 1) Does the study involve human participants?  Yes  No
- 2) Are the participants prospectively assigned to an intervention?  Yes  No
- 3) Is the study designed to evaluate the effect of the intervention on the participants?  Yes  No
- 4) Is the effect being evaluated a health-related biomedical or behavioral outcome?  Yes  No

Note that if the answers to the 4 questions are yes, your study meets the NIH definition of a clinical trial, even if...

- You are studying healthy participants
- Your study does not have a comparison group (e.g., placebo or control)
- Your study is only designed to assess the pharmacokinetics, safety, and/or maximum tolerated dose of an investigational drug
- Your study is utilizing a behavioral intervention

If yes to all 4 questions, please confirm that the research team is familiar with and agrees to comply with the investigator requirement to register the study on the ClinicalTrials.gov database. Additionally, the approved consent document(s) must be uploaded to the ClinicalTrials.gov database  Yes  No

For any assistance with registration of your trial or the requirements, please contact [contact]

## 1. Objectives

**Purpose:** The purpose of the research is to determine how people residing in New Mexico counties and cities are experiencing the phenomenology of the COVID-19 pandemic and a rating of quality of life. The specific questions of interest are:

1. How are rural-living vs. urban-living people responding physically and mentally to the crisis?
2. What strategies of resilience are employed by people living in rural vs. urban counties?
3. What are perceptions of access to critical supplies and services in urban vs. rural counties;
4. How is the availability and use of technology used for news, reliable information, and communication? And;
5. What alterations in daily life self-care, care of others, commerce, and valued routines in urban vs. rural counties are occurring?

**There is a critical need** to determine the impact of the COVID-19 emergency on the comprehensive well-being of people as they are living through the emergency and the extended sequelae of the emergency period.

### Specific Aims:

Aim 1: Extensively evaluate the perceived quality of life (QOL) of urban vs. rural living people during the COVID-19 emergency, thereby assessing similarities and differences in QOL impact during the national health emergency.

Aim 2: Evaluate the daily lived experience of people living in rural and urban areas during the health emergency in regard to biopsychosocial factors impacting the well-being of individuals and families, including access to services and resources for health, finances, technology, news and information use, use of time, and psychosocial support.

Aim 3: Determining use of resilience strategies (protective factors) of urban vs. rural living people during the national health emergency.

### Hypothesis

Rural-living people experience the health emergency with a significant impact to well-being (physical, psychological, and social) as compared to urban people.

## 2. Background

The state of New Mexico and the entire nation have entered an *unprecedented health emergency* created by the COVID-19 virus; affecting the lives of all people, many of whom were significantly unprepared for the disruptions the emergency created in daily life. *Rural residents are at increased risk* from effects of the emergency due to numerous disadvantages as compared to urban living people (i.e. critical care access, food insecurity, social isolation). Very little is known about how people are living through a national emergency event affecting *all people* of the nation. Therefore, a *significant gap* in knowledge exists:

Preliminary research from China on mental health and quality of life during the COVID-19 emergency (Zhang & Ma, 2020; Wang, et al. 2020) find mixed results. Zhang (2020) reports the pandemic as a mild stressful impact, although 52.1% (N=263) of respondents

## COVID 19 Effects on Quality of Life

in one city also felt “horrified and apprehensive” due to the pandemic; however Wang et al. (2020), found over 50% of respondents (N=1210) from 194 cities were experiencing moderate to severe psychological effects of the pandemic.

Although there are no peer reviewed published studies in the United States at this time, the Henry J. Kaiser Family Foundation issued a briefing from a Kaiser poll indicating that 45% of adults in the U.S. have reported their mental health has been negatively impacted due to worry and stress over the virus, and noting those living in social isolation and low income may be disproportionately affected by the health emergency. One study on people living in the United States with rheumatic diseases (N=530) reported stresses and anxiety/fear/worry over access to medications, health care, sadness and loneliness with social distancing (Michaud, et al., 2020). Additionally, multiple mental health information links are now prominent on the Centers for Disease Control website, indicative of the severity of the mental health impact of the pandemic.

Completion of the research acquires new knowledge in the field on how people have experienced a national emergency and thus, is innovative. As an outcome, the knowledge will be utilized by those who have roles in developing national and community responses to improve planning and preparation for future national health emergencies. As a result, rural and urban-living stakeholders and those in governance will be better informed when making decisions to ameliorate the risk-factors and disproportionate burden of national emergencies affecting access to critical supplies, services, and commerce. The research will be replicable in the region and nation.

### **3. Study Design**

The exploratory research will be conducted using mixed methods: qualitative and quantitative approaches. The quantitative approach incorporates demographic information and a valid and reliable health quality of life measure from the World Health Organization (WHOQOL-BREF) used with permission. The WHOQOL-BREF is 26 question instrument measuring perceptions of physical, psychological, social, and environmental health. Responses can be compared between subject cohorts for specific characteristics, correlations, and effects. The qualitative approach incorporates a researcher developed open-ended semi-structured interview instrument gauged to study the phenomenology of how people in urban vs. rural contexts are experiencing the COVID-19 pandemic.

None of the investigators will be blinded during the investigation.

### **4. Inclusion and Exclusion Criteria**

Inclusion Criteria: Adult residents of New Mexico of any gender, gender identity, and ethnic origin speaking the English language, living in rural or urban/suburban locations, ages 18-85, will be eligible to participate in the study. Screening for eligibility will occur at time of making contact. Pregnant women are not excluded from participation because this special status is not relevant, the research poses less than minimal risk, and pregnancy is not the focus of the study.

## COVID 19 Effects on Quality of Life

Exclusion: Incarcerated individuals, children, and those with inability to give consent will be excluded from the study. Assessing the capacity of consent of the person is limited due to the method of surveying by telephone or internet. The investigators will endeavor to ensure ability to consent by questioning the potential subject about their understanding of the research, their understanding of the right to consent or withdraw (i.e. understanding choice), their ability to reason, clarity in decision-making, and noticing confusion by the potential participant, or noticing cues of impairment (i.e. difficulty with orienting to temporal events, days, months). Investigators will be familiar with principles of competency for consent including items from the MacArthur Competency Assessment Tool for Clinical Research (MacCAT-CR).

Residents of New Mexico may be excluded if they are unable to speak English since the WHOQOL-BREF may not be available in other languages of the resident. The researchers will be preparing for future research using Spanish translations, but will not be modifying the protocol at this time in order to be timely in gathering the urgent data.

### *Number of Subjects*

Up to 300 participants (150 in each group: urban or rural) will be recruited to take the WHOQOL-BREF. The qualitative interview will continue until saturation is reached, not to exceed 300 interviews. The sample is adequate to power the study to reach a power of 0.8.

## **5. Study Timelines**

Consented participants will be enrolled in the study until April 30, 2021 at which time the study will be closed to enrollment. Participants will be given a WHOQOL-BREF survey twice during the health emergency, anticipating timing to be once during the emergency and once post-emergency. Analysis of de-identified collected data will continue after April 30, 2021 to complete statistical operations and preparation of manuscripts.

## **6. Study Endpoints**

The primary study endpoint will occur by April 30, 2021 at the end of the grant funding.

## **Research Setting**

This is a prospective study. Research will be conducted via telephonic or wireless technologies enabling individual contact with prospective participants. Researchers will be based in HSC offices or, from work at home locations as determined by the HSC as necessary due to the pandemic. Prospective participants will be reached via public directories available across every New Mexico county.

## **7. Resources Available**

[name] is well qualified to direct the study as a principal investigator. She has been a principal investigator on collaborative multi-center, multi-state federal grants

## COVID 19 Effects on Quality of Life

including those from the Patient Centered-Outcome Research Institute. *She has significant experience in conducting UNM approved and indigenous IRB approved research on the Navajo Nation regarding impact of arthritis.*

Co-Investigator [name] has previous IRB approved research experience on disability in agriculture and quality of life of farmers and ranchers with health conditions. She is very knowledgeable about rural health issues of New Mexico communities.

Co-Investigator [name], has previous IRB approved research experience in rehabilitation and interventional technologies.

To Be Determined: Research Coordinator: The team will hire a research coordinator to assist with adhering to timeline, facilitating filing of interim and final reports, monitoring budget with the assistance of the OT Division Administrative Manager, and other administrative responsibilities. The Research Coordinator will not be handling identifiable information of participants

Four Occupational Therapy Graduate Students who have completed HIPAA & CITI training will assist with collection of data. They will be trained in the appropriate use of screenings, eligibility criteria, and collection tools.

The research team anticipates a 20 hour a week effort (all team members combined) to contact potential research participants for up to 48 weeks. Approximately 300 participants are needed to achieve sufficient power for the study.

No dedicated offices or laboratories will be necessary to complete the research.

## 8. Prior Approvals

This study is registered with the National Institutes Clinical Trials registry.

No radiation will be used in the study, no animals will be used in the study, and no biological specimens are being collected.

## 9. Multi-Site Research

N/A

## 10. Study Procedures

Contact information for accessible prospective participants will be derived from publicly available directories for the 33 counties of New Mexico. The research team will be attempting to obtain a representative sample of all New Mexico residents using proportional systematic sampling with a random start point, and a sampling interval of 10, to make contact via telephonic or internet technologies. The goal is to obtain a probability sample for residents by age, gender, ethnicity, and geographic distribution into two cohorts: urban and rural residents. It is desirable to generate a sample that closely mirrors the population of New Mexico.

Researchers making contact will use a contact script to introduce themselves, the purpose of the research, and determine the interest of the person in participating. If a person is

## COVID 19 Effects on Quality of Life

interested in participating a screening for eligibility will be conducted. Once the screening is complete and eligibility is determined, an informed consent process will follow. The consent process will describe the research and the rights of the participant to participate or withdraw from the study. The prospect will be advised the interview will be recorded using a hand-held digital recorder with a phone audio pickup. If consent is obtained verbally, the collection of data will commence. A copy of the consent will be delivered to the participant via U.S. post, facsimile, or electronically.

Demographic data: name, address, county, preferred contact phone and/or email, age, gender/gender identity, education level, socio-economic status, and ethnicity. (see demographic data intake form).

Assessments: WHOQOL-BREF (see attached) 27 item survey questions will be read to the subject and response recorded. The WHOQOL-BREF measures the biopsychosocial perceptions of individuals about quality of life. A semi-structured interview will follow that will ask questions about the emergency experience of the COVID-19 health emergency regarding perceptions of daily life routines, availability of needed resources, and preferred sources of information regarding COVID-19. (See semi-structured interview form).

Once the assessment data is obtained, the subject will be thanked and then invited to participate in a post-event data collection using the WHOQOL-BREF and interest in participating in a focus group at a future time.

Post-event assessment: WHOQOL-BREF. Prior to the conclusion of the study, participants will be asked to perform a post-event assessment of quality of life.

Focus group: Prior to conclusion of the study, a facilitated focus group comprised of two groups (urban or rural) will be assembled to present the qualitative themes gained from the semi-structured interview. Subjects selected for the focus group will be representative of the state's population by age, gender, socio-economic, geography, and ethnicity. Some individuals may represent more than one characteristic.

## 11. Data Analysis

Qualitative Analysis: Data for qualitative analysis will come from the semi-structured interviews. Each interview will be anonymized using an identification number. The key between subject and identification number will be held on a secure encryption device held in a secure location of the primary investigator's office. The interview will be transcribed verbatim using a transcription application from Olympus. Investigators will examine the transcripts to ensure accuracy, resolve misspellings, or resolve missing sections due to poor sound reproduction. The transcriptions will be sent to the participant via U.S. post, facsimile, or email in order to check for accuracy (member checking). Transcripts will be analyzed using resources from the CTSC utilizing qualitative analysis software to help with organizing, sorting, and arranging the

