## COVID 19 Effects on Quality of Life

materials for analysis. Codes will be generated via the software and used to assist investigators in developing thematic material. Team members will confer and reach consensus on the results (peer debriefing). Iteratively, the meaning of the content will be derived and prepared for reporting. The de-identified transcripts and data will be subjected to auditing by an outside auditor with expertise in qualitative research methods. All media: paper and electronic will be held in secure offices within locked metal filing cabinets. Electronic media will have further security using devices meeting federal standards for encryption and password protection.

Quantitative analysis will be analyzed by [name] with assistance from a graduate student employee using SPSS.

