## COVID 19 Effects on Quality of Life

Extreme care will be taken to protect the data using UNM HSC IT recommended technology for encryption and password protection. The team will purchase a portable storage device (jump drive) for that purpose. Only the PI and Co-PIs will have physical control of storage devices. Identifiers will be held separately from the storage device, in the PIs secure office, in a secure and locked metal filing cabinet. Each participant will be given a unique code for data analysis purposes. In every instance, identifiable information is secured separately from the data and participant code. Identifying data will be held for three years, per IRB recommendation, and thereafter destroyed using a secure shredding bin. The identifying data includes the audio recordings of participants. De-identified data will be kept indefinitely for manuscript purposes. Data will not be transferred electronically and work with the data will occur on non-networked computers owned by the division. No identifiable health information is being collected.

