## 16.Risks to Subjects

The investigators anticipate minimal risk to subjects being surveyed and interviewed for the study. However, due to the severity and extent of the COVID-19 health emergency, they do anticipate some participants may express extreme stress, depression, or anxiety. The investigators will have a readily available and sharable list of mental health resources, financial resources, and food bank resources to mitigate distress caused by the emergency. Reversibility of risks depends on the length of the health emergency and improvement in socio-economic status for some participants. These may be outside the direct influence of investigators, but efforts to mitigate will be offered through providing reliable information and referral. Through careful handling of data, as described above, investigators will minimize the risk of breach of confidentiality and/or privacy. The risks will be described in the consent.

Since participants will be giving individual interviews, it is not likely the procedures will put non-participants at risk. However, if participants disclose being victims of domestic violence or perpetrating domestic violence or performing acts of abuse or neglect of children or elderly co-habitants, it is necessary in the consent to give warning that as health professionals, the investigators would be bound to report such disclosures per state law.

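### Returning verbatim transcripts by fax or email contradicts the protocol's ban on electronic transfer, and the risk section does not consider where a returned transcript may arrive

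*Protocol*

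**What the plan says.** Protocol section 11 (Data Analysis) describes the path of the interview text. "Each interview will be anonymized using an identification number", then "The interview will be transcribed verbatim using a transcription application from Olympus". Investigators check the transcript for accuracy, and after that "The transcriptions will be sent to the participant via U.S. post, facsimile, or email in order to check for accuracy (member checking". The same section adds "All media: paper and electronic will be held in secure offices within locked metal filing cabinets".

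Protocol section 14 (Data Management/Confidentiality) sets the handling rules: "Data will not be transferred electronically and work with the data will occur on non-networked computers owned by the division". It also says "In every instance, identifiable information is secured separately from the data and participant code", and it accepts that what a person discloses, together with where they live, could reveal who they are.

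Protocol section 16 (Risks to Subjects) requires the consent to warn of a reporting duty "if participants disclose being victims of domestic violence or perpetrating domestic violence or performing acts of abuse or neglect of children or elderly co-habitants". It relies on the data handling already described to keep the risk of a confidentiality breach low, and it judges risk to non-participants unlikely because interviews are individual.

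The SAP (Data Analysis Plan, Qualitative) records that the researcher confirmed transcripts against the audio. It does not mention member checking.

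**The concern.** A transcript is study data, and section 14 bars electronic transfer of data without qualification. A team member who returns a transcript by fax or email, as section 11 allows, breaks that bar. The confidentiality protection that section 16 relies on is then not the one the study delivers.

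The content makes this more than a drafting matter. The transcript is verbatim, and the protocol accepts that it might record violence or abuse within a household. A home address, fax machine or mailbox may be shared with the person whom a disclosure concerns. The risk section considers the interview itself but not a written copy that arrives later.

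**Working it through.** No sample size, power or error rate bears on this point, and the plan states no figure to reproduce. The check sets the passages side by side.

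1. **Is the transcript covered by the transfer rule?** Section 11 says that the data for the qualitative analysis come from the interviews, so transcripts are data. The rule in section 14 is not limited to identifiable data, so replacing the name with an identification number does not take a transcript outside it.

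2. **Which routes conflict?**

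| Route in section 11 | Ban on electronic transfer (section 14) | Non-networked computers (section 14) |
|---|---|---|
| Post | No conflict | No conflict |
| Fax | Conflict | Depends on how the fax is sent |
| Email | Conflict | Conflict: email cannot leave a machine that is off the network |

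Two of the three routes contradict the ban.

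3. **Is there an exception elsewhere?** None was found in protocol sections 10, 11, 14, 16, 18 and 19 or in the SAP. Section 19 allows secured storage inside the institution's systems, but it does not deal with sending transcripts out.

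4. **Does the risk section cover the returned copy?** Section 16 names the possible disclosures, refers back to the data handling, and rests its view of non-participants on the interviews being individual. It does not mention the transcript's return.

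5. **Is there a delivery safeguard?** Section 10 collects a preferred telephone number or email address, but as demographic data and not as a check that the route is private. The available text describes no opt-out from receiving a transcript, no withholding of sensitive passages and no encryption for the return.

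6. **How many transcripts?** Under Number of Subjects, interviews stop at saturation and cannot exceed 300. So 300 is an upper limit on transcripts returned, and the number sent by fax or email is some unknown part of it. The documents give no disclosure rate and no rate of shared contact points, so the number of harmful exposures cannot be calculated.

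7. **Does accuracy depend on returning transcripts?** Only in part. The investigator check in section 11 and the audio confirmation in the SAP are both separate from member checking.

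**The case against.** The strongest reply is that section 11 offers alternatives. A team that always posts the transcript satisfies both section 11 and the ban on electronic transfer. That stands: a reader might infer that the two sections cannot both be followed, and the documents do not support this. What remains is that section 11 authorises two routes that section 14 forbids.

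A reader might also infer that any addressed transcript, including a posted one, breaks the separation rule, since staff must use the key to match a name to the content. The rule sits among provisions on storage devices and locked cabinets and concerns how the team secures its holdings. It does not say that a participant's own words are never returned to that participant. A breach there is an inference, and the point does not rest on it.

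The wording on abuse is conditional and serves the reporting warning. The interview topics in section 10 are daily routines, access to resources and sources of information, so such disclosures would be incidental. It goes too far to say that the protocol expects them. Nor does the household risk contradict the statement about non-participants, because the harm would fall mainly on the participant.

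Finally, the consent pages were not available for this review, nor were the intake and interview forms. A delivery preference or opt-out may be stated there. That could answer the household concern, but it would not remove the conflict between sections 11 and 14.

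**Conclusion.** The contradiction is established from the text: fax and email, two of the three permitted routes, conflict with an unqualified rule in section 14, and post does not. It applies to whatever part of at most 300 transcripts goes by those routes.

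Exposure within a household is a reasonable inference and not a documented event. It assumes that some disclosures occur, that some contact points are shared, and that the consent material holds no safeguard. A reader might want to put a count on it, but any count would rest on an assumed disclosure rate and on a ceiling in place of the actual number of interviews. The point should be corrected because section 16 relies on data handling that section 11 does not follow, and because the correction is cheap.

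**What to change.** Reconcile protocol sections 11, 14 and 16.

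- Either remove fax and email from section 11, or state in section 14 that member checking is the one permitted electronic transfer and how it is protected.
- Send a transcript only to participants who opt in at consent and name a private delivery route.
- Withhold any disclosure of the kind named in section 16 from the copy unless the participant agrees to its inclusion.
- Add the returned transcript to the risks considered in section 16. If the consent material already has a delivery safeguard, refer to it there.

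The cost is wording in the protocol and consent script, and slightly less complete member checking because some participants will decline. The investigator accuracy check and the audio confirmation remain. Telephone read-back need not be required instead: the second contact is by invitation, reading back would add call time, and a call can also be overheard at home.
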